- Suppressed plasma viral load result (≤ 20 copies/mL) within the past 6 months, and no unsuppressed viral load during that time. Routine viral load monitoring has only recently been implemented at AKTH. By enrolling only patients with recent evidence of viral suppression, we will reduce the impact of ongoing HIVassociated viral replication in non-adherent persons as a contributing cause of immune activation and therefore end-organ complications, including kidney disease.
- Completing Aim 1 of the study **AND** having a repeat single uACR value between 30-300 mg/g (based on first morning voided specimen) at time of Aim 2 screening to confirm eligibility.
- \leq 1+ hematuria on urine dipstick
- eGFR ≥ 60 ml/min/1.73m² based on serum creatinine value obtained during Aim 1 AND based on repeat serum creatinine value obtained at time of Aim 2 screening to confirm eligibility (NOTE: eGFR for Aim 1 and Aim 2 calculated using the CKD-EPI-Cr-CyC equation).

AND

• If female, non-pregnant (documentation of negative urine pregnancy test) and not breastfeeding/lactating. In addition, if female (with reproductive potential), needs to be reliably/consistently be receiving contraceptives (including documentation of being receiving reliable/consistent contraceptives; including enrolment in family planning/consultative services).

Exclusion criteria:

- eGFR of < 60 ml/min/1.73m²
- uACR < 30 mg/g or > 300 mg/g (on Aim 2 screening)
- K+ > 5.0 mmol/L, or reasons to be concerned about hyperkalemia
- History of diabetes mellitus (would qualify for treatment with an ACEi/ARB) [NOTE: Standardized diabetes screening procedure (fasting or random glucose ≥ 6.1 mmol/L)]
- ≥ 2+ hematuria on urine dipstick (assuming they might have glomerulonephritis from chronic active hepatitis B and/or C as both conditions can also cause albuminuria/proteinuria)
- Poorly controlled hypertension (Mean BP readings > 160/110 mm Hg in past 6 months)
- Persistent symptomatic hypotension (BP < 90/60 mm Hg) (on 2 or more successive readings)
- Known history of chronic congestive heart failure
- Initial screening uACR value > 300 mg/g plus urine dipstick ≥ 2+ for protein
- Currently receiving an ACEi and/or ARB;

OR

• Lack of suitability as a study candidate (i.e. active substance use disorder, active use of potentially nephrotoxic medication(s) [e.g. traditional medicines, etc.] and/or history of poor compliance [e.g. multiple missed scheduled clinic appointments, etc.])

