4.0 Enrollment/Randomization

Participants will be enrolled at Aminu Kano Teaching Hospital (AKTH), Kano, Nigeria. All HIV-positive ART-experienced (≥6 months on ART) individuals found to meet the inclusion criteria will be approached by a study coordinator for enrollment into this study. The study coordinator will describe the purpose of the study and the included activities and will review the informed consent with the potential participant. Those who provide written informed consent will be enrolled.

Aim 2 will be a randomized double-blind (both participants and study physicians involved in the conduct of this study), placebo-controlled study to minimize crossovers and bias in the classification of outcomes and potential adverse effects secondary to ACE-inhibitor therapy (lisinopril), which we anticipate will be minimal. We will apply block randomization to ensure balance of baseline uACR between randomization arms. Using this block randomization, stratifying patients at time of study enrollment, we plan to enroll equal numbers of patients in each stratum.

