NOTE: We also plan to collect and store plasma, sera, and urine specimens from all screened / consenting aim 1 study participants for future analyses that we will perform by obtaining separate/additional grant funding; specifically storing specimens (-80°C) for future biomarker association and other relevant translational studies, and as a backup DNA source for quality control. We will also seek ancillary/supplemental funding to conduct 12- and 24-month follow-up of consenting Aim 1 patients for Aim 3 outcomes.

Aim 2 Study Procedures

Study Medication: Participants in the intervention arm will be given lisinopril at a starting dose of 5 mg/day at time of Aim 2 enrollment. Participants in the control arm will receive a matched placebo. Participants who are found to have symptomatic hypotension and/or new onset /persistent grade 3 (or higher) hyperkalemia after taking study medication (as evaluated at day 3 (safety phone call), week 1, month 1, or during an unscheduled visit will be removed from the study.

Participants who tolerate the initial study dose (5 mg/day or placebo) will be increased to 10 mg/day lisinopril (or matched placebo) at their one (1)-month study visit. All study participants having a dose change/escalation from 5 to 10 mg active medication (or matched placebo), will also (as was done following study enrollment) undergo safety monitoring in the form of a 3-day post dose escalation safety phone call, a 1-week post dose escalation study visit for blood draw/safety evaluation, and 1-month post dose escalation study visit for blood draw/safety evaluation. Those who do not tolerate an increase to the 10 mg/day dose will be returned to the 5 mg/day dose, while those who are able to tolerate an increase to the 10 mg/d dose will be closely monitored for

adverse events and re-assessed (see below) at their 3-month study visit for a possible dose escalation to 20 mg/d of lisinopril.

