Angioneurotic edema: Angioneurotic edema, which occurs in 0.1-0.2% of patients, usually develops within the first week of therapy but can occur at any time. This life-threatening adverse effect also occurs with angiotensin II receptor blockers but to a lesser extent. Any patient with a history of angioneurotic edema, whether related to an ACE inhibitor, angiotensin receptor blockers (ARBs), or another cause, should not be given an ACE inhibitor. (NOTE: any allergic reaction that is "definitely related" or "possibly related to study medication" that involves generalized urticaria OR angioedema with intervention indicated OR symptoms of mild bronchospasm is classified as a grade 3 acute allergic reaction and an SAE is needed and the participant is immediately unblinded, and if on active study medication (ACEi or ARB) it is to be discontinued immediately, and this allergic reaction is to be documented in their medical record. If the participant has acute anaphylaxis OR life-threatening bronchospasm OR laryngeal edema; this is a grade 4 acute allergic reaction and an SAE is needed and the participant is immediately unblinded, and if on active study medication (ACEi or ARB) it is to be discontinued immediately, and this allergic reaction is to be documented in their medical record.

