If the participants eGFR keeps on falling despite holding the study medication, and no other discernible causes for the kidney insult can be identified, we will discontinue tenofovir (TDF) and switch/substitute with abacavir (ABC). Please note that in Nigeria and other similar resource-constrained settings, the, initiation of abacavir (ABC) does not require genetic testing; specifically, HLA-B*5701 testing; the risk variant associated with risk for ABC-associated hypersensitivity reactions. To maintain integrity of the study, participants will be informed and consented about the chance of switching their ARV medications when the need arises. In addition, we have emphasized that in a significant proportion of cases, individual ARV medications will be substituted (only one medication in the ART regimen will be changed (i.e. TDF to ABC) and not the entire regimen, i.e. from first to second line ART regimens.

2. Evaluation of subjects for adverse events

Subjects will be evaluated by a study physician at each visit for AEs. In addition, additional safety monitoring visits in the form of scheduled clinic visits and phone calls have been included and can be summarized as follows:

- a) Study enrollment/initiation of study medication (5 mg of lisinopril or matched placebo) (**study entry/enrollment**);
 - 3-day safety phone call (post initiation of study medication (or matched placebo) evaluating for possible adverse events (and if during phone safety check screening there is any suggestion of a possible adverse event, then the participant will be instructed to come

in to clinic for immediate evaluation including blood draw and blood pressure check)

- 7-day safety clinic visit (blood draw plus blood pressure check)
- 1-month safety clinic visit (blood draw plus blood pressure check)
- Unscheduled study visit (study participants to contact study personnel at any time and if have signs/symptoms at suggestive of an adverse event, they will come to clinic for immediate assessment)
- b) Dose escalation of study medication (increase from 5 mg/d of lisinopril or matched placebo to 10 mg/d) (scheduled to take place at the 1- month study visit);

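### The protocol says nobody with a history of angioedema should receive an ACE inhibitor, but the Aim 2 eligibility criteria do not exclude such people

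*Combined protocol and SAP*

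**What the plan says.** The angioneurotic edema paragraph under Anticipated risks in Section 6.0 gives an unqualified rule against ACE inhibitors: "Any patient with a history of angioneurotic edema, whether related to an ACE inhibitor, angiotensin receptor blockers (ARBs), or another cause, should not be given" (the sentence then names this drug class). The same paragraph calls the reaction life-threatening and says that it "usually develops within the first week of therapy but can occur at any time". The rest of that paragraph deals with what happens after a reaction: an SAE report, unblinding, stopping active drug and recording the allergy.

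The Aim 2 criteria are in Section 3.0. The only exclusion naming this drug class is "Currently receiving an ACEi and/or ARB". A general clause, "Lack of suitability as a study candidate", follows, illustrated by substance use, nephrotoxic medication and poor compliance.

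Section 4.0 states: "Aim 2 will be a randomized double-blind (both participants and study physicians involved in the conduct of this study), placebo-controlled study". Section 5.0 states: "Participants in the intervention arm will be given lisinopril at a starting dose of 5 mg/day at time of Aim 2 enrollment". After the first dose, Section 6.0 schedules first a "3-day safety phone call (post initiation of study medication (or matched placebo) evaluating for possible adverse events" and then a "7-day safety clinic visit (blood draw plus blood pressure check".

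**The concern.** The safety rule and the eligibility rule do not match. Someone can satisfy every named Aim 2 criterion and still be a person to whom the protocol says the study drug should not be given. Whether that person is kept out depends on someone asking about the history, or the patient volunteering it, and on staff then applying a sentence in the safety section or the discretionary clause.

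What is at stake is avoidable exposure to a drug that the protocol itself contraindicates, for a reaction that it regards as life-threatening. Inference is not at stake: the point has no bearing on power or type I error.

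**Working it through.** The plan gives no figure to reproduce here, so the check is mainly a comparison of text.

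**1. Is the rule anywhere in the criteria?** The Aim 2 exclusions are: eGFR below 60; uACR outside 30–300 mg/g; potassium above 5.0 mmol/L or concern about hyperkalemia; diabetes; hematuria of 2+ or more; poorly controlled hypertension; persistent symptomatic hypotension; chronic heart failure; high initial uACR with dipstick protein; current ACE inhibitor or ARB use; and lack of suitability. The inclusion criteria cover Aim 1 participation, viral suppression, uACR, hematuria, eGFR, pregnancy, breastfeeding and contraception. None mentions angioedema, hypersensitivity or a past reaction. By contrast, hyperkalemia, hypotension, pregnancy and heart failure each have a named criterion.

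**2. Would another item catch the person?** The current-use exclusion does not reach someone who stopped the drug because of angioedema. The suitability clause could be used, but its examples do not point to allergy history. The Aim 1 procedures in Section 5.0 promise a full medical evaluation; the comorbidities listed for collection (opportunistic infections, syphilis, cancer, hypertension, other cardiovascular disease) include no angioedema or drug-allergy item. The manuals and case report forms named in Appendix A are not in the documents, so whether screening already asks cannot be checked.

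**3. Why does the rule belong in eligibility?** It is written in terms of the drug, and study physicians are blinded to the drug. Before dosing, it can be obeyed only by not starting blinded medication, which amounts to not enrolling the person. Lisinopril starts at enrollment and angioedema is said usually to appear in the first week. The day-3 call and day-7 visit can detect a reaction but cannot prevent the exposure.

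**4. Scale.** From Section 8.0, 280 are randomised 1:1, so 280 / 2 = 140 receive lisinopril. Let p be the share of otherwise eligible people with the history and d the share of those detected and excluded before randomisation. Both are assumptions; the documents give neither. The 0.1–0.2% in Section 6.0 is the rate of angioedema on therapy and cannot stand in for p.

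The share with the history among those randomised is q = p(1 − d) / (1 − pd), and the expected number on lisinopril is 140q. For example, with p = 1% and d = 50%: q = 0.005 / 0.995 = 0.005025, and 140q = 0.704.

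| | p = 0.1% | p = 0.5% | p = 1% |
|---|---|---|---|
| d = 0 (upper bound) | 0.14 | 0.70 | 1.40 |
| d = 50% | 0.070 | 0.351 | 0.704 |
| d = 90% | 0.014 | 0.070 | 0.141 |

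These are people with the history assigned to the drug, not reactions. The protocol gives no reaction rate for such people.

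**The case against.** The strongest reply is that the protection already exists. Section 6.0 states the rule without qualification, in a part of the protocol introduced as describing risks and how they will be minimised. If blinding means that the rule can only be followed by withholding study medication, then it already works as a bar before dosing, and what remains is a rule placed in the wrong section. Section 6.0 also has trained staff review the risks with patients in the information and consent forms, and consent is taken again for Aim 2, so a past reaction could come up then. The consent pages were removed from the copy reviewed, so their content cannot be held against the plan. Finally, the scenarios rest on assumed inputs and span about a hundredfold.

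Some of this stands. The protocol is not silent, the consent discussion is a real opportunity, and the scenarios show only that the number is small; they do not measure risk. However, no step in the available documents is said to ask about this history, and a discussion of risks is not a screening criterion. Staff who apply the eligibility list as written would admit a person whom another section says should not receive the drug. That two parts of one protocol disagree does not depend on how many people are affected.

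**Conclusion.** The concern holds. The contraindication is stated in the safety section, is missing from the Aim 2 criteria, and is not reliably covered by any other named criterion. Confidence in this textual mismatch is high. Whether an affected person would in practice be missed cannot be determined without the screening forms and consent pages.

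The number affected is probably very small: at most 1.4 of 140 on lisinopril under the most unfavourable assumptions used (1% prevalence, no detection), and below one in every scenario with detection of half or more. The case rests on severity and easy prevention, not on frequency. It should be fixed as a patient-safety matter. No wider pattern is implied: prior ACE inhibitor cough has no exclusion either, but the protocol does not treat cough as life-threatening and provides a switch to losartan.

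**What to change.** Add to the Aim 2 exclusions: *history of angioedema from any cause, or prior angioedema or hypersensitivity reaction to an ACE inhibitor or ARB*. The part on hypersensitivity goes slightly beyond the rule in Section 6.0 and can be dropped without losing the main correction. Confirm that the screening form asks the question before randomisation, and add it if not. Ask participants already enrolled, and refer any positive answer to the Study Oversight Committee and the Study Safety Committee.

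The cost is one line, possibly one screening question, review of the amendment by both IRBs, and the time to question current participants. At an assumed 1% prevalence the loss is at most 280 × 0.01 = 2.8 people if counted against the randomised sample. Counted against the roughly 460 expected to be eligible (Section 1.2) it is 460 × 0.01 = 4.6, leaving about 455 for 280 places, so the target need not change.

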	baseline (Repeat ScR and monitor	1 week and monitor closely for signs of worsening kidney function
	closely for signs of worsening kidney	
	function; i.e. decreased urinary output,	eGFR worsens by 20-29% when compared
	fatigue, palpitations, dyspnea,	to baseline (Repeat eGFR within 1 week and
	lightheadedness, and/or generalized	monitor closely for signs of worsening kidney
	fatigue/malaise). If repeat sCr normalizes	function; i.e. decreased urinary output, fatigue,
	(< 1.2x below baseline value)	palpitations, dyspnea, lightheadedness, and/or
	(ESCALATE)	generalized fatigue/malaise). If repeat eGFR
		improves/normalizes (i.e. is reduced < 20%
	NOTE: Any time sCr increase 1.3 -1.8x	when compared to baseline) (ESCALATE)
	the upper limit of normal (ULN) OR sCr	
	increases between 1.3 - 1.49x from	NOTE: A 10-20% decrease in eGFR in
	baseline; this constitutes a grade 2 event.	baseline constitutes a grade 2 event; and
	Any time sCr increase 1.8 – 3.49x the	when any patient experiences a > 10% decline
	ULN OR sCr increases between 1.5 –	in eGFR (from baseline), their renal function
	1.99x from baseline; this constitutes a	needs to be more intensively monitored. A
	grade 3 event (and requires an SAE to be	decrease in eGFR between 30-50% (from
	completed)	baseline) constitutes a grade 3 event (and
	Anytime sCr increases by ≥ 1.3-fold;	requires an SAE to be completed)
	immediately HOLD study medication;	Anytime eGFR diminishes by > 30% from
	look for other possible	baseline; immediately HOLD study
	etiologies/contributing factors; and monitor	medication; look for other possible
	closely; repeating BMP within 1 week; If	etiologies/contributing factors; and monitor
	repeat sCr normalizes (< 1.2-fold below	closely; repeating eGFR within 1 week; If
	baseline value) (ESCALATE); but if sCr	repeat eGFR improves/normalizes (< 20%
	elevations persist by ≥ 1.3-fold from	below baseline value) (ESCALATE); but if
	baseline; continue to HOLD study	eGFR reductions persist by ≥ 30% from
	medication; involve the SOC/SSC; as	baseline; continue to HOLD study
	study medication may need to be	medication; involve the SOC/SSC; as study
	discontinued and AE report done	medication may need to be discontinued
	NOTE: All study participants resolution	and AE report done
	NOTE: All study participants receiving dolutegravir (DTG)-based ART may	Any study participant experiencing a drop
	experience a sustained increase in serum	in eGFR (at any time) to < 50 ml/min/1.73m ²
	creatinine (sCr) (up to 0.2 mg/dL) that	(using CKD-EPI-Cr-CyC equation);
	may persist for up to 48 weeks (or	immediately HOLD study medication; look
	possibly longer) so to account for these	for other possible etiologies/contributing
	potential modest changes in renal	factors; and monitor closely; repeating eGFR
	function, all safety events involving kidney	within 1 week; involve the SOC/SSC; as
	function deemed "possibly" or "definitely	study medication may need to be discontinued
	related" to study medication among DTG-	and AE report done
	treated study participants will be	
	evaluated and graded using serum	
	creatinine (sCr) measurements.	
Step 2 to 3	Same as above for Step 1	Same as above for Step 1
(10 mg/d		
20 mg/u)		

Step 23to 4 (20 mg/d ↑ to 40 mg/d)	Same as above for Step 1	Same as above for Step 1

Risks of prescribed combination antiretroviral therapy (ART) (specifically tenofovir (TDF):

All eligible/enrolled aim 2 study participants will be receiving ART for 6+ months, and we anticipate that a significant proportion (i.e. > 80%) of them will be receiving tenofovir (TDF)-based regimens. We mention this because of the potential adverse events that have been attributed to the nucleotide reverse transcriptase inhibitor TDF, namely kidney toxicity which may manifest as a reduction in eGFR. These potential TDF-associated kidney manifestations that include reduced eGFR, Fanconi's syndrome, etc. are due to tubular (rather than glomerular) insults; and they often present within the first 1-2 years following TDF initiation and based on our preliminary analysis of enrolled aim 1 study participants (January 2019), the majority of aim 1 study participants (from which we will be screening/enrolling for aim 2) have been receiving ART for considerably longer periods of time (i.e. mean duration of ART > 8 years).

Management of Worsening Renal Function Among Study Participants receiving tenofovir (TDF)-based ART regimens:

At an eGFR of 30-49 ml/min/1.73m², patients receiving a TDF-based regimen should ideally have their dose modified to 300 mg q48 hours. If the eGFR falls further into the 10-29 ml/min/1.73m² range, the dose should be adjusted to 300 mg q72 hours. However, these recommended dose adjustments are difficult to implement as most of the ARV regimens are dispensed as fixed drug combinations (FDCs). In addition, adjusting the dose to alternate day dosing makes things very challenging logistically and may promote poor adherence due to the increased likelihood of patients missing/forgetting doses. Therefore, at an eGFR 30-49 ml/min/1.73m², the standard of care (SOC) is to switch tenofovir (TDF) to an alternative NRTI (i.e. abacavir (ABC)); realizing that if the person is receiving abacavir plus lamivudine (3TC), the 3TC will need to be renally adjusted given that it is renally excreted (and 3TC dosing will be adjusted/modified per established standards). The on-site study team is to notify/involve the SOC/SSC of any/all participants with worsening renal function (as outlined above) so they can assist in the management, tracking and development of AE/SAE forms (as needed).

Management of worsening renal function among persons receiving TDF plus study medication (lisinopril/matched placebo)

The study team needs to immediately investigate for a potential cause of declining eGFR (i.e. looking for pre-renal causes such as dehydration, post-renal causes (prostatic obstruction, nephrolithiasis, and/or intra-renal causes such as initiation of new potentially nephrotoxic medications (such as traditional medicines). We should not wait until the eGFR drops to <50 ml/min/1.73m² before we discontinue the study medication. Further clinical decisions RE: management is to be based on the cause of declining eGFR. Please refer to "Table 3: Aim 2 Study Medication (Matched Placebo) Dose Titration Algorithm" for specific management details. In addition, in terms of specific management, if a study

participant's calculated eGFR drops < 50 ml/min per 1.73m², the team will need to complete an AE report (send to the SOC/SSC) and update as needed. At this level of kidney function decline (< 50 ml/min per 1.73m²), the study participant's study medication needs to be immediately held and the patients need to be thoroughly evaluated for other potentially contributing causes of worsening kidney function; i.e. volume contraction (dehydration, sepsis, GI bleeding, etc.), obstruction, nephrotoxin (any potentially nephrotoxic medication (i.e. aminoglycosides, etc.), IV contrast, traditional medicines, etc.), and/or other causes (rhabdomyolysis, etc.). During this time of study medication hold, the participant needs to be monitored closely and have their blood pressure, electrolytes (specifically their K+), and kidney function (serum creatinine and calculated eGFR) monitored as deemed necessary by the study team in consultation with the SOC/SSC. Patients will need to have their eGFR reevaluated within 7 days (or sooner at the discretion of the treating clinician). If their eGFR has not stabilized/improved, with no other apparent etiology for worsening kidney function, consider holding tenofovir (TDF)(if on TDF-based ART) and/or dose reducing study medication (on a case-by-case basis; also in close collaboration/communication with the SOC/SSC). Depending on the kidney function/other parameters (i.e. K+, etc.), the study participant may need to be switched to an alternative ART regimen (i.e. switch TDF to ABC) and continue to monitor; and if their study medication was dose reduced, the on-site team will continue to monitor them closely to determine next steps; i.e. permanently discontinue study medication and/or other medications or attempt to resume study medication and titrate up the dose as deemed appropriate.

If the participants eGFR keeps on falling despite holding the study medication, and no other discernible causes for the kidney insult can be identified, we will discontinue tenofovir (TDF) and switch/substitute with abacavir (ABC). Please note that in Nigeria and other similar resource-constrained settings, the, initiation of abacavir (ABC) does not require genetic testing; specifically, HLA-B*5701 testing; the risk variant associated with risk for ABC-associated hypersensitivity reactions. To maintain integrity of the study, participants will be informed and consented about the chance of switching their ARV medications when the need arises. In addition, we have emphasized that in a significant proportion of cases, individual ARV medications will be substituted (only one medication in the ART regimen will be changed (i.e. TDF to ABC) and not the entire regimen, i.e. from first to second line ART regimens.

2. Evaluation of subjects for adverse events

Subjects will be evaluated by a study physician at each visit for AEs. In addition, additional safety monitoring visits in the form of scheduled clinic visits and phone calls have been included and can be summarized as follows:

- a) Study enrollment/initiation of study medication (5 mg of lisinopril or matched placebo) (**study entry/enrollment**);
 - 3-day safety phone call (post initiation of study medication (or matched placebo) evaluating for possible adverse events (and if during phone safety check screening there is any suggestion of a possible adverse event, then the participant will be instructed to come

in to clinic for immediate evaluation including blood draw and blood pressure check)

- 7-day safety clinic visit (blood draw plus blood pressure check)
- 1-month safety clinic visit (blood draw plus blood pressure check)
- Unscheduled study visit (study participants to contact study personnel at any time and if have signs/symptoms at suggestive of an adverse event, they will come to clinic for immediate assessment)
- b) Dose escalation of study medication (increase from 5 mg/d of lisinopril or matched placebo to 10 mg/d) (scheduled to take place at the 1- month study visit);
 - 3-day safety phone call (post initiation of study medication (or matched placebo) evaluating for possible adverse events (and if during phone safety check screening there is any suggestion of a possible adverse event, then the participant will be instructed to come in to clinic for immediate evaluation including blood draw and blood pressure check)
 - 7-day safety clinic visit (blood draw plus blood pressure check)
 - 1-month safety clinic visit (blood draw plus blood pressure check)
 - Unscheduled study visit (study participants to contact study personnel at any time and if have signs/symptoms at suggestive of an adverse event, they will come to clinic for immediate assessment)
- c) Dose escalation of study medication (increase from 10 mg/d of lisinopril or matched placebo to 20 mg/d) (scheduled to take place at the 3- month study visit);
 - 3-day safety phone call (post initiation of study medication (or matched placebo) evaluating for possible adverse events (and if during phone safety check screening there is any suggestion of a possible adverse event, then the participant will be instructed to come in to clinic for immediate evaluation including blood draw and blood pressure check)
 - 7-day safety clinic visit (blood draw plus blood pressure check)
 - 1-month safety clinic visit (blood draw plus blood pressure check)
 - Unscheduled study visit (study participants to contact study personnel at any time and if have signs/symptoms at suggestive of an adverse event, they will come to clinic for immediate assessment)

- d) Dose escalation of study medication (increase from 20 mg/d of lisinopril or matched placebo to 40 mg/d) (scheduled to take place at the 5- month study visit);
 - 3-day safety phone call (post initiation of study medication (or matched placebo) evaluating for possible adverse events (and if during phone safety check screening there is any suggestion of a possible adverse event, then the participant will be instructed to come in to clinic for immediate evaluation including blood draw and blood pressure check)
 - 7-day safety clinic visit (blood draw plus blood pressure check)
 - 1-month safety clinic visit (blood draw plus blood pressure check)
 - Unscheduled study visit (study participants to contact study personnel at any time and if have signs/symptoms at suggestive of an adverse event, they will come to clinic for immediate assessment

Once participants complete their 4-month study visit including having their study medication dose (or matched placebo) increased to 40 mg/d and undergo the additional safety visits as outlined in b) and c) above, all study participants will continue to undergo scheduled safety/tolerability assessments (study visits during which time blood draws and blood pressure evaluations will be performed at a minimum of every 3 months.

Additionally, all participants will be counseled to contact study staff or come in at any time (including unscheduled visits) if they feel ill, feel that their urine output may have diminished, and/or have questions about potential side effects or about the care and treatment they are receiving. An interval history of medical events and potential adverse events will be obtained at these visits. This information will continue to be collected for three (3) months after the participant has stopped the study medication. Monitoring for AEs (including unanticipated AEs) will be performed by reviewing patient laboratory and clinic data and querying patients at each follow-up visit about the occurrence of complications since the patient's previous visit. All AEs will be characterized in terms of "*relatedness*" to study intervention (i.e. study medication) as follows: "*definitely related*", "*possibly related*", "*unable to assess relatedness to study medication*." In terms of severity, all AEs will be graded on the basis of severity (standard 1-5 grading scale using the DAIDS Toxicity Grading Scale; version 2.1, July 2017).

B. Adverse Event Reporting

Definitions

Definitions are per the January 2007 Guidance on Reviewing and Reporting Unanticipated Problems Involving Risks to Participants or Others and Adverse Events, Office on Human Research Protection (OHRP) Guidance. https://www.hhs.gov/ohrp/regulations-and-policy/guidance/reviewing-unanticipatedproblems/index.html

Adverse Event

An *adverse event (AE)* is any untoward or unfavorable medical occurrence in a human study participant, including any abnormal sign (for example, abnormal physical examination or laboratory finding), symptom, and/or disease, temporally associated with the participant's involvement in the research, whether or not this event is considered related to the participant's participation in the research.

Serious Adverse Event

A serious adverse event (SAE) is any AE that is:

- fatal or results in death
- life-threatening
- requires or prolongs hospital stay
- results in persistent or significant disability or incapacity
- results in congenital anomalies or birth defects
- an important medical event*

*Important medical events are those that may not be immediately life threatening but are clearly of major clinical significance. Based on expert medical judgment, this important medical event may jeopardize the subject's health and may require medical or surgical intervention to prevent one of the other outcomes listed above

"Unanticipated Event" Involving Risk to Participants or Others

An "Unanticipated Event" is any incident, experience, or outcome that meets ALL of the following criteria:

- it is unexpected (in terms of nature, severity, or frequency), given the research procedures that are described in the IRB-approved research protocol and informed consent document and the characteristics of the participant population being studied;
- it is "*definitely related*" or "*possibly related*" to study medication/participation in the research, where "*possibly related*" means that there is a reasonable possibility that the incident, experience and/or outcome may have been caused by the procedures involved in the research, and
- it suggests that the research places participants or others at a greater risk of harm (including physical, psychological, economic, and/or social harm) related to the research than was previously known or recognized.

Pre-Existing Condition

A "pre-existing condition" is one that is present at the start of the study. A "pre-existing condition" will be recorded as an AE if the frequency, intensity, or character of the condition worsens during the study period.

Adverse Event (AE) Reporting Period

The study period during which AEs must be tracked and reported is defined as the period from the initiation of study procedures to study completion.

Post-Study AEs

All unresolved AEs will be followed by the investigator until the events are resolved, the participant is lost to follow-up, or the AE is otherwise explained. At the last scheduled visit, the investigator will instruct each participant to report any subsequent event(s) that the participant, or the participant's personal physician, believes might reasonably be related to participation in this study. The investigator will notify the R3 Study Oversight Committee (SOC) and the Study Safety Committee (SSC) of any death or AE occurring at any time after a participant has discontinued or terminated study participants will be monitored/tracked for any AEs for 3 months after they complete the study; and any/all AEs that occur up to 3 months post study completion will be recorded/captured).

NOTE: The R3 **Study Oversight Committee (SOC)** will consist of the MPIs (Drs. [name] and [name]), the Trial Coordinator, The Program Manager, and the in-country lead investigator ([name]). The **Study Safety Committee (SSC)** will function independently to maintain the integrity of investigations into AEs and will be overseen by two Clinical Trials Safety Specialists, namely Drs. [name] and [name].

Recording of AEs

At each contact with the participant, the Co-Investigators and/or Research Coordinators will seek information on AEs by specific questioning and, as appropriate, by examination. Information on AEs will be recorded in the source documents as well as on the AE log case report form (CRF). All signs, symptoms, and abnormal diagnostic procedure results relating to the same event will be recorded under one diagnosis name.

All adverse events (AE), regardless of severity, that is reported to any study team member and meets the criteria for an AE, will be documented. This documentation will include the date the event occurred or began, the duration of the event (including resolution date when applicable), and the date and way in which the event was reported. Any clinical or other documentation to corroborate the event will be included in the report, as well as any determination of relatedness. All study staff will have access to an electronic structured report form in REDCap for these purposes. The form will include common side effects of lisinopril, and losartan and classifications based on seriousness, expectedness, and relatedness (i.e. "*definitely related to study medication*", "*possibly related to study medication*", "*definitely not related to study medication*", or "*unable to assess if related to study medication*"). Unanticipated AEs will include adverse reactions that are not consistent (nature or severity) with the available information on lisinopril or losartan. The Division of AIDS Table for Grading the Severity of Adult and Pediatric Adverse Events (DAIDS AE Grading Table), Version 2.1, July 2017, will be used to

determine clinical and laboratory grades of any/all grade 1 or higher events (including signs and symptoms, laboratory abnormalities, and diagnoses).

Anticipated AEs

The following AEs are anticipated in HIV-positive adults that are initiated on combination antiretroviral therapy (ART) and are not considered Unanticipated Problems. As such, they would be considered Non-Reportable Events. Please note that most of these side effects are typically seen within the first 1-4 weeks following ART initiation. Given that we will be enrolling ART-experienced patients (on ART >6 months), we anticipate encountering very few (if any) such events in the context of our R3 study. Note that the designation "Non-reportable" does not imply that the event is not an SAE but relates to the regulatory definition of Unanticipated Problems as provided in previous section.

- Gastrointestinal: Nausea and diarrhea (mild/grade 1) related to antiretroviral (ARV) medications; as mild to even moderate GI symptoms are often seen in persons in the first 1-6 weeks (sometimes up to 8 weeks) following initiation of most ART regimens, but this diarrhea/nausea is typically self-limited and resolves on its own. On rare occasions, it can continue/progress to grade 2 or higher and any persistent GI symptoms seen in R3 patients (all need to be on ART for 6+ months) will be captured/tracked if grade 1 or higher.
- **Hepatic**: Mild (grade 1 or 2) elevations in total bilirubin among persons receiving the boosted protease inhibitor atazanavir/ritonavir (as atazanavir is also known to cause asymptomatic elevations in unconjugated hyperbilirubinemia [**NOTE**: We will report when grade 2 or higher or deemed "clinically significant" by study team personnel].
